11 STATISTICAL METHODS

11.1 Sample Size Determination

Approximately 150 patients are planned to be enrolled in this study. This study was designed to demonstrate the efficacy of WVE-210201 compared to placebo on a clinical endpoint, NSAA.

The sample size determination for the NSAA endpoint was based on the following assumptions:

- Two-sample t-test to test for statistical significance of treatment difference

- 1:1:2:2 placebo 3 mg/kg, placebo 4.5 mg/kg, WVE-210201 3 mg/kg, and WVE-210201 4.5 mg/kg randomization ratio
- Standard deviation of change in NSAA from baseline to 48 weeks⁵⁵ of 4.5
- Treatment difference of change in NSAA from baseline to 48 weeks of 3.0 between WVE-210201 and placebo
- Dropout rate of 10%
- Two-sided significance level of 5%

With these assumptions, a sample size of 150 patients provides 88% power to detect a difference of 3 in the change in NSAA from baseline to 48 weeks. The treatment difference of 3 was selected as it is equal to the average 1-year decline observed in longitudinal natural history studies^{55,56}.

The power of the dystrophin endpoint was based on the following assumptions:

- Two-sample t-test to test for statistical significance of treatment difference
- 150 patients randomized 1:1:2:2 placebo 3 mg/kg, placebo 4.5 mg/kg, WVE-210201 3 mg/kg, and WVE-210201 4.5 mg/kg
- Standard deviation of change in dystrophin protein level from baseline to 46 weeks of 3.0%
- Treatment difference of change in dystrophin protein level from baseline to 46 weeks of 4.0% between WVE 210201 and placebo
- Dropout rate of 10%
- Two-sided significance level of 5%

With these assumptions, the power is greater than 99% to detect a difference of 4% in the change in dystrophin level from baseline to 46 weeks.

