Summaries of the posterior distribution for the treatment difference in dystrophin compared to placebo at each time point for each arm will be provided including the probability that each treatment is superior to placebo at each time point, $\Pr(\theta_{T,j} > 0)$, as well as mean and 95% credible intervals.

The dystrophin analysis will be supplemented with dystrophin data from the ongoing Open-label extension study to the Phase 1 trial (WVE-DMDX51-002). These results will be available at the time of the first dystrophin interim analysis.

Missing dystrophin data can result from intercurrent events which include discontinuation of the study and non-evaluable biopsies. Previous pivotal studies in DMD, including exon skipping therapies, have had low study discontinuation rates (e.g. 0.6% and 2.7%) so it is anticipated that missing data resulting from study discontinuation will be limited (^{57,58}). With the selected estimand, missing dystrophin results due to study discontinuation will be handled using baseline imputation. Non-evaluable dystrophin will be addressed using imputation under the assumption of missing-at-random (MAR). The regression method for monotone missing data will be used for the multiple imputation with baseline dystrophin as a covariate and imputation stratified by treatment arm.

There will be two interim dystrophin efficacy analyses and a final dystrophin efficacy analysis. The dystrophin treatment effects will be declared significant at the interim or final analyses using a gatekeeping strategy where the WVE-210201 4.5 mg/kg arm is assessed first and, if significant, the WVE-210201 3 mg/kg arm is assessed. To account for the three possible analyses of the dystrophin treatment effects, a Bonferroni-level adjustment will be applied. A one-sided, significance threshold of $1 - (0.025/3) = 0.991667$ will be used for the Bayesian posterior probability of superiority of each dose compared to placebo. If successful for WVE-

210210 4.5 mg/kg, the same threshold will be used for WVE-210210 3 mg/kg. Specifically, success will be declared for WVE-210201 4.5 mg/kg if

1. $\Pr(\theta_{2,1} > 0) > 0.991667$ at the first dystrophin interim analysis,
2. $\Pr(\theta_{2,2} > 0) > 0.991667$ at the second dystrophin interim analysis, or
3. $\Pr(\theta_{2,3} > 0) > 0.991667$ at the final dystrophin analysis.

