11.3.2.2 Analysis of North Star Ambulatory Assessment (NSAA)

Another primary objective is to evaluate the efficacy of WVE-210201 by assessing changes in the NSAA. Therefore, the primary efficacy endpoint for the EU and Japan and the key secondary endpoint for the United States and Other regions is the change in NSAA from baseline over 48 weeks. The treatment policy estimand which assesses the effect of treatment initially assigned at baseline (regardless of adherence to the planned course of treatment) will be used. The analysis population will be the ITT population. The main estimator will be a Bayesian progression model (BPM) to compare the change in NSAA between patients treated with WVE-210201 and placebo treated patients^{59,60}. The placebo data from this study will be augmented with historical control data via a Bayesian meta-analytic approach.

The BPM assumes a non-parametric rate of progression of the NSAA for placebo patients and a proportional rate of slowing NSAA progression for the treated patients relative to the placebo patients at each time point. The model will include covariate effects to measure differences in the rates of progression based on patient-specific baseline covariates. Additionally, random patient variability will be accounted for using patient-level random effects of the rate of NSAA progression. Borrowing from historical control data to augment the placebo arm information will entail including a random data source effect to model the between-source variability in NSAA progression rates.

The NSAA analysis will be independent of the dystrophin analysis described in [Section 11.3.2.1](#). Let the NSAA at visit j for patient i be Y_{ij} , for $j = 0, \dots, 4$ and $i = 1, \dots, n$. The Y_{i0} observation corresponds to the baseline visit. Visits $j = 1, 2, 3, 4$ refer to the post-baseline visits (each separated by 12 weeks). Let X_i be a vector of dimension C of baseline covariates for patient i that have been standardized. The DPM is

$$Y_{ij} = \gamma_i + \exp(\theta_{t(i)} + \eta_i + \alpha X_i + \delta_{s(i)}) \sum_{k=0:j} \beta_k + \epsilon_{ij}; \\ \epsilon_{ij} \sim N(0, \sigma_{t(i),s(i)}^2).$$

Patient-specific random effects, $\gamma_i, i = 1, \dots, n$, represent the patient-specific mean NSAA at the time of randomization.

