The residual errors for the individual observations, $\epsilon_{ij}, i = 1, \dots, n$ and $j = 0, \dots, 4$, are modelled as independent normal distributions with a treatment arm and source-specific standard deviation of $\sigma_{t(i),s(i)}$.

Missing NSAA data can result from intercurrent events which include discontinuation of the study and loss of ability to complete any NSAA activities. With the selected primary estimand, missing NSAA assessments or NSAA assessments collected after randomized therapy discontinuation will be imputed using a control-based imputation strategy for treated patients. Placebo patients will have missing observations imputed assuming MAR. The loss of the ability

to complete any NSAA activities will be recorded as 0 on the case report forms and used in the analysis.

The posterior probability that the DRR is less than 1 will be assessed to determine significance of the WVE-210201 NSAA treatment effect. Superiority on slowing the rate of decline on NSAA will be declared if the posterior probability that either 1) the pooled WVE-210201 treatment effect ($\theta_1 = \theta_2$; if the low dose has not been dropped) or 2) the WVE-210201 treatment effect θ_2 (if randomization to the WVE-210201 3 mg/kg has been stopped) is superior to placebo and slows the rate of NSAA progression is greater than 0.975:

$$\Pr(\exp(\theta_2) < 1) > 0.975.$$

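### As worded, the NSAA rule gives a missed visit in a boy still on WVE-210201 a control-based value but treats placebo gaps as missing at random: a modest, conservative dilution that one clause would remove

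*Combined protocol and SAP*

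**What the plan says.** Section 11.3.2.2 adopts a treatment policy estimand, which "assesses the effect of treatment initially assigned at baseline (regardless of adherence to the planned course of treatment"). On missing data it first names sources: "Missing NSAA data can result from intercurrent events which include discontinuation of the study and loss of ability to complete any NSAA activities". It then sets the rule for the active arms: "missing NSAA assessments or NSAA assessments collected after randomized therapy discontinuation will be imputed using a control-based imputation strategy for treated patients". For the comparator, "Placebo patients will have missing observations imputed assuming MAR". A boy who can no longer do any item is scored 0, and that score is analysed, so this group is settled separately.

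The section names no control-based variant (jump to reference, copy reference and so on), does not say whether the reference includes the historical controls, and has no separate rule for a visit missed by a boy still receiving study drug.

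Section 11.3.2.1 treats dystrophin differently. There, study discontinuation leads to baseline imputation, whereas "Non-evaluable dystrophin will be addressed using imputation under the assumption of missing-at-random (MAR"), with imputation stratified by treatment arm. The cause of the gap decides the method.

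**The concern.** A missing assessment cannot have been collected, so the phrase about discontinued therapy can qualify only the second item in the sentence. The first item, missing assessments, is unqualified. A boy still being infused who misses the Week 24 test would have that score generated from control behaviour, although he is under his assigned treatment and may have observed scores on either side. A placebo boy with the same gap is imputed under MAR.

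The two arms are therefore handled asymmetrically for gaps unrelated to stopping treatment, and a real effect is diluted. NSAA is the primary endpoint for the EU and Japan and the key secondary endpoint for the United States and other regions. The progression model shares one rate ratio across visits, so an imputed intermediate visit feeds into the main estimate as well.

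**Working it through.** **Inputs.** From section 11.1: 150 patients allocated 1:1:2:2 (50 placebo in total, 50 per active dose), difference 3.0, SD 4.5, dropout 10%, two-sided 5%, stated power 88%. From section 11.3.2.2: the two doses are pooled for NSAA unless randomization to 3 mg/kg is stopped. Section 11.1 also says of the 3-point difference that "it is equal to the average 1-year decline observed in longitudinal natural history studies", so the planned effect amounts to a complete halt of decline. The rate of missed visits on drug is **not in the documents**; 2%, 5% and 10% are assumed.

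**Step 1: reproduce the plan's figure.** Two-sample t-test, noncentrality = d / (SD × √(1/n₀ + 1/n₁)).

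- One dose against all placebo after dropout, 45 vs 45: 3.0 / (4.5 × √(2/45)) = 3.16, df 88, power 87.9%. This matches the stated 88%.
- Doses pooled, 90 vs 45: 3.0 / (4.5 × √(1/45 + 1/90)) = 3.65, df 133, power 95.2%. This is the default NSAA comparison, so it is the base used below.

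**Step 2: upper bound, jump-to-control at Week 48.** If a share q of treated Week 48 values is moved to the placebo mean, the expected difference is 3.0 × (1 − q).

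| q | Effect | Power, pooled 90 vs 45 | Power, one dose 45 vs 45 |
|---|---|---|---|
| 0 | 3.00 | 95.2% | 87.9% |
| 2% | 2.94 | 94.4% | 86.5% |
| 5% | 2.85 | 93.1% | 84.4% |
| 10% | 2.70 | 90.4% | 80.4% |

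**Step 3: only Weeks 24 and 36 missed.** The formula in step 2 does not apply, because a t-test on Week 48 change ignores those visits. A simplified proportional-slowing model (linear decline, independent errors, change measured from a fixed baseline) weights each visit by time squared. With times 0.25, 0.5, 0.75 and 1, the sum of squares is 0.0625 + 0.25 + 0.5625 + 1 = 1.875. Weeks 24 and 36 carry (0.25 + 0.5625) / 1.875 = 43% of the weight. With 10% missed at both visits, the effect is 3.0 × (1 − 0.10 × 0.433) = 2.87, and pooled power is about 93.4%.

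**Step 4: milder variant and the remedy.** The simulation used random slopes, five visits, and post-baseline visits missed completely at random at 10% each, with a true effect of 3.0:

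- Jump-to-reference: 2.70–2.71
- Copy-reference: 2.89–2.97 (residual SD 2.0 and 1.0 respectively), a loss of about 1–4%
- MAR within own arm: about 3.0

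**Step 5: no drug effect.** The control and active means coincide, so the two imputation rules agree in expectation. There is no shift and no type I inflation from this source.

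**Step 6: how much power the remedy recovers.** MAR does not restore lost information. At worst, if 10% of Week 48 values in both arms contributed nothing, the pooled comparison would be 81 vs 40.5 (90 × 0.9 and 45 × 0.9), with power 93.0%. So at 10% missed the gain over jump-to-control is at least 93.0 − 90.4 = 2.6 percentage points and at most 95.2 − 90.4 = 4.8.

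**The case against.** The strongest reply is contextual. The preceding sentence speaks of intercurrent events such as leaving the study. A skipped visit is not an intercurrent event, so the authors probably had dropouts in mind. That is a fair reading of intent, but it does not settle the text: the list is introduced as open, and if dropouts alone were meant, on-drug gaps have no rule at all. Either way the same clause is needed.

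Second, wholly missed tests may be rare. Dosing is weekly with a ±2-day window, and NSAA is done on the dosing day or within the preceding 24 hours (Table 1 footnotes; section 8.7.2). The only related figures are study-discontinuation rates of 0.6% and 2.7% in earlier trials (section 11.3.2.1). These are not missed-visit rates, but at those values the jump-to-control loss is only 3.0 × 0.006 = 0.02 to 3.0 × 0.027 = 0.08 points, with pooled power of 95.0% and 94.1%. This stands: the 10% row is an extreme, not a forecast.

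Three stronger readings are tempting and are not supported.

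- *A reader might infer a power loss from 88% to 80%.* That is one dose against placebo. The default analysis pools the doses, and the placebo arm is also augmented with historical controls.
- *A reader might infer that no estimand could justify a placebo-like value.* The estimand and the missing-data assumption used to estimate it are different things. A conservative assumption in the active arm can be defended as a choice.
- *A reader might infer that the rule buys no robustness.* Boys doing badly may skip tests, and section 6.2.4 allows doses to be held without discontinuation, so a missed test may be informative or fall while drug is interrupted. Control-based imputation gives some protection there.

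**Conclusion.** The point holds as a wording defect with a predictable direction. Followed as written, the rule assigns control-based values to on-drug gaps in the active arms only, and dilutes a true effect. The size is modest: at most 0.06 to 0.30 points of the planned 3.0 if 2% to 10% of treated Week 48 values are missed on drug and the variant is jump-to-control, with pooled t-test power falling from 95% to 94–90%. It is about 0.13 points if only Weeks 24 and 36 are missed at 10%, and 0.03 to 0.11 points under copy-reference with 10% missed at each visit.

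These figures rest on an assumed missed-visit rate, an unnamed variant, visits missed at random, and a t-test or simplified linear model in place of the Bayesian progression model. The bias is conservative and does not threaten a positive claim. The case for acting is that a rule in a primary analysis should be unambiguous before unblinding, and that the protocol already separates causes of missingness for dystrophin.

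**What to change.** In section 11.3.2.2 and the SAP:

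1. Limit control-based imputation of missing NSAA values in the active arms to those missing after permanent study-drug discontinuation or study withdrawal.
2. Treat intermittent gaps in boys still on assigned treatment as MAR within their own arm. In the progression model they can be left missing. This mirrors the rule for non-evaluable biopsies.
3. Name the control-based variant and state whether its reference group includes the historical controls.
4. Keep control-based imputation of all treated gaps as a sensitivity analysis, to cover informative missed visits and visits missed during dose holds.

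The cost is one clause, a line of definition and one extra sensitivity run. No data collection or procedure changes. The downside is a slightly less conservative primary analysis, which the sensitivity analysis makes visible.

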11.3.2.3 Secondary Efficacy Analyses

The secondary efficacy endpoints will be analyzed in the ITT population using a Bayesian progression model analogous to the model described for the analysis of the NSAA endpoint.

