This Phase 2/3 study includes several planned interim efficacy analyses. Interim analyses of dystrophin will determine if efficacy is demonstrated prior to study conclusion and if adaptations to treatment arm allocation or clinical efficacy analyses are warranted. In the event that an interim dystrophin analysis results in a statistically significant finding in the dystrophin level in favor of WVE-210201, the study will continue and patients will remain in the Double-blind Treatment Period (up to 48 weeks) to assess clinical outcomes and other endpoints.

The lower age requirement (5 years) was chosen to ensure that patients would be definitively diagnosed with DMD and able to comply with required clinical assessments and testing procedures. While patients may first exhibit symptoms at 2.5 years, many are not diagnosed until 5 years of age⁴. In addition, the use of corticosteroids prior to this age is less common and varies greatly by region, impacting the ability to control for this important concomitant medication in this global study. It is known that progressive muscle degeneration in DMD eventually leads to loss of ambulation in most patients by 10 to 12 years of age⁵. Pathologically, the myofiber breakdown, necrosis and inflammation that results from the lack of dystrophin production in DMD gives rise to tissue fibrosis and fat cell replacement⁴³. The Sponsor is proposing to identify a homogenous population of patients for this efficacy and safety study with the intention of enrolling patients aged 5 to 12 years who may putatively have a more limited extent of tissue destruction, thereby maximizing the likelihood that they may benefit from treatment and reducing variability.

Other important outcome assessments in DMD, such as respiratory function tests, muscle function and strength tests, including timed function tests, will be included as additional secondary endpoints.

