4.3 Study Endpoints

4.3.1 Double-blind Treatment Period

Study Endpoints: The primary and key secondary efficacy endpoints differ by region. All other endpoints are the same across regions.

Primary Efficacy Endpoint

- Change from baseline in dystrophin level (% normal dystrophin) assessed by Western blot of muscle tissue (United States/Other regions, as applicable)
- Change from baseline in North Star Ambulatory Assessment (NSAA) through 48 weeks (EU/Japan)

Secondary Efficacy Endpoints

- Key secondary endpoint - Change from baseline in NSAA through 48 weeks (United States/Other regions, as applicable)
- Key secondary endpoint - Change from baseline dystrophin level (% normal dystrophin) assessed by Western blot of muscle tissue (EU/Japan)
- Change from baseline in upper limb proximal strength assessed by hand held myometry through 48 weeks
- Change from baseline in 4-stair climb (4SC) through 48 weeks
- Change from baseline in the 10-meter walk/run test through 48 weeks

- Change from baseline in forced vital capacity (FVC; % predicted) through 48 weeks
- Change from baseline in the 95th percentile of stride velocity through 48 weeks

Exploratory Efficacy Endpoints

- Change from baseline in Pediatric Quality of Life Inventory (PedsQLTM)-neuromuscular module at 48 weeks
- Change from baseline in Pediatric Quality of Life Inventory (PedsQLTM)-Generic Core Scale module at 48 weeks
- Change from baseline in individual NSAA items through 48 weeks
- Change from baseline in respiratory function (peak flow rate [PFR], cough peak flow [CPF]) through 48 weeks
- Change from baseline in PUL 2.0 through 48 weeks
- Time to milestone events (loss of ambulation, loss of self-feeding, requirement of daytime ventilation on a regular basis)
- Changes from baseline in daily activity as measured by a wearable device measure

Safety, Pharmacokinetic and Pharmacodynamic Endpoints

- Adverse events, laboratory values, physical exams and vital signs
- Changes from baseline in cardiac functions by ECHO
- Concentration of WVE-210201 in plasma
- Concentration of WVE-210201 in muscle
- Exon-skipping by RT-PCR in muscle tissue
- Dystrophin localization by immunofluorescence

4.3.2 *Open-label Treatment Period*

- Long-term efficacy, safety, and PK of WVE-210201

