5.1 Inclusion Criteria

1. Patient and/or parent or legal guardian must have the ability and be willing to provide written informed consent prior to any study-related procedures
2. Diagnosis of DMD based on clinical phenotype with increased serum creatine kinase
3. Documented mutation in the Dystrophin gene associated with DMD that is amenable to exon 51 skipping
4. Ambulatory male, able to walk independently for at least 10 meters in 10 seconds or less at the time of Screening visit (performed as part of the NSAA)
5. Age of ≥ 5 and ≤ 12 years at time of randomization
6. Willing and able to comply with scheduled visits, drug administration plan, laboratory tests, study restrictions, and all study procedures, including undergoing the biopsy procedures
7. Stable pulmonary and cardiac function, as measured by:
 - a. Reproducible percent predicted forced vital capacity (FVC) $\geq 50\%$
 - b. Left ventricular ejection fraction (LVEF) $>55\%$ in patients <10 years of age and $>45\%$ in patients ≥ 10 years of age, as measured (and documented) by echocardiogram
8. Currently on a stable corticosteroid therapy regimen, defined as initiation of systemic corticosteroid therapy occurred ≥ 6 months prior to Screening, and no changes in dosing ≤ 3 months prior to Screening visit
9. Adequate deltoid muscle at Screening to perform open muscle biopsies
10. Sexually mature males must be willing to use contraception for the duration of the study, if the patient is sexually active
11. Patient and caregivers must agree not to post any study-related information on social media

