8.7 Efficacy Assessments

8.7.1 *Dystrophin Quantification by Western Blot*

Levels of dystrophin may be quantified by Western blot in the muscle tissues collected at baseline and at one of three postbaseline time points, according to [Section 4.1](#).

The amount of restored dystrophin protein from muscle tissues will be evaluated using a validated Western blot method, according to a detailed validation protocol.

8.7.2 *Functional Assessments*

Functional assessments that are included in both NSAA and Timed Function Tests, will only be administered once per timepoint.

Functional assessments must be performed pre-dose on: Weeks 1, 12, 24, 36 48, 60, 72, 84 and 96 (on the dosing day or up to 24 hours prior to the indicated dosing day) in the order listed below:

See the [Table 1](#), [Table 2](#) and the Study Manual for additional information

- NSAA (will also be done at screening)
- PUL 2.0
- Timed function test 4-stair climb
- Hand-held myometry
- Pulmonary function tests (PFR, CPF, and FVC); FVC will be done at screening as well.

PedsQL ([Section 8.7.3](#)) assessments must be performed pre-dose on Weeks 1, 48, and 96 (on the dosing day or up to 24 hours prior to indicated dosing day), in the following order:

- PedsQL-NMM and GCS
- NSAA
- PUL 2.0
- Timed function test 4-stair climb

- Hand-held myometry
- Pulmonary function tests (PFR, CPF, and FVC); FVC will be done at screening as well.

8.7.2.1 *North Star Ambulatory Assessment*

The NSAA is a validated unidimensional scale, designed for measuring motor function in ambulatory boys with DMD^{45,46}. The scale is suitable for multicentric global studies and is widely used internationally as a relevant functional assessment for patients with DMD. The scale was specifically designed for ambulant children with DMD. NSAA includes 17 items, ranging from standing (item 1) to running (item 17), that are necessary to remain functionally ambulant. The scale includes items assessing abilities, such as head raise and standing on heels that can be present in the early stages of the disease and other activities such as hopping, or running that are generally never fully achieved in untreated DMD boys⁴⁷.

Each item is scored on a 3-point scale using simple criteria:

2 - Normal; achieves goal without any assistance

1 - Modified method but achieves goal independent of physical assistance from another person

0 - Unable to achieve independently

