The total score is the sum of the individual item scores. The score can range from 0, if no activities can be achieved independently, to 34, if all the activities can be achieved without any assistance. The scale is generally completed in a maximum of 15 minutes.

8.7.2.2 *Timed Function Tests*

The time to climb 4 standard-sized stairs will also measure lower limb motor function in ambulatory patients. Other timed-function tests, 10-m walk/run and rise from floor will be performed by the patient only once as part of NSAA, and will not be re-administered. These tests will be recorded on both NSAA and TFT scales.

8.7.2.3 *Performance of Upper Limb (PUL 2.0) Test*

The PUL test is an assessment tool that evaluates upper limb function in ambulatory and non-ambulatory DMD patients and was developed through a collaborative international group including boys with DMD and their families. The PUL test was designed with a conceptual framework reflecting the progression of weakness and the natural history of functional decline in DMD⁴⁸.

8.7.2.4 *Hand-held Myometry*

Upper limb proximal strength will be assessed by handheld myometry^{49,50}.

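### Do the two timed tests need a stated scale and inability value before they can be analysed like the NSAA?

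*Combined protocol and SAP*

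**What the plan says.** Section 4.3.1 lists "Change from baseline in 4-stair climb (4SC) through 48 weeks" and the matching change for the 10-m walk/run among the secondary endpoints, without unit or transformation. Section 8.7.2.2 describes the stair test as a time: "The time to climb 4 standard-sized stairs will also measure lower limb motor function in ambulatory patients". The 10-m walk/run is performed once, within the NSAA, and the same section adds: "These tests will be recorded on both NSAA and TFT scales".

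The NSAA has a defined worst value. An item that cannot be done is scored "0 - Unable to achieve independently", and for the total, "The score can range from 0, if no activities can be achieved independently, to 34". Section 11.3.2.2 constrains each 12-week step of the progression model to be zero or negative. It imputes missing NSAA values under MAR for placebo boys and by a control-based method for treated boys, and it enters total loss of NSAA function as 0.

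Section 11.3.2.3 then covers the remaining secondary endpoints in one sentence, in the ITT population, "using a Bayesian progression model analogous to the model described for the analysis of the NSAA endpoint".

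**The concern.** An analogous model can carry over the idea of a worst score, but not a number. Seconds rise as a boy worsens and have no upper limit, so neither the floor of 0 nor the sign constraint transfers unchanged. A boy who loses the 10-m run has a defined 0 on the NSAA item and no stated value on the timed record.

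Inability is foreseeable. Boys may be up to 12 years old at randomisation, and section 2 notes "loss of ambulation in most patients by 10 to 12 years" of age. The entry criterion "able to walk independently for at least 10 meters in 10 seconds or less at the time of Screening visit" covers the 10-m test only. Stairs have no entry rule and are first tested on Day 1, so a randomised boy could lack a baseline stair time.

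At stake is the reported size of the slowing on these two tests if the drug works, and the risk of a later challenge that the inability value was picked to suit the result.

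**Working it through.** **Inputs.** The plan gives no figure for either timed test, so there is none to reproduce. Two inputs come from it: the illustrative rate ratio of 0.75 in section 11.3.2.2, and the sample size in section 11.1 (150 × 0.9 = 135, or 45 placebo v 90 active at 1:2). Everything else below is assumed.

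**Step 1, hand arithmetic in seconds.** Boys who can still do the test slow by 2.0 s (placebo) or 1.5 s (active), a ratio of 0.75. Boys who lose the test start at 8 s and are given the cap V. With proportion p losing the test and slowing c among the rest, mean change = (1 − p) × c + p × (V − 8).

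Example, 10% v 5% loss, V = 30:
- placebo: 0.90 × 2.0 + 0.10 × 22 = 4.00
- active: 0.95 × 1.5 + 0.05 × 22 = 2.525
- ratio: 2.525 / 4.00 = 0.631

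| Loss, placebo / active | V = 15 | V = 30 | V = 45 | V = 60 |
|---|---|---|---|---|
| 10% / 10% | 0.820 | 0.888 | 0.918 | 0.936 |
| 10% / 7.5% | 0.765 | 0.759 | 0.757 | 0.755 |
| 10% / 5% | 0.710 | 0.631 | 0.595 | 0.575 |
| 5% / 7.5% | 0.850 | 1.012 | 1.110 | 1.175 |

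The cap sets the weight given to loss of the test relative to slowing. When loss falls by the same 25% as the rate (second row), the cap hardly matters. The last row passes 1 because more treated boys lose the test, which is a real harm and not an artefact.

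Scale matters even with nobody unable (baseline 5 s):
- seconds: 1.5 / 2.0 = 0.75
- log time: ln(6.5/5) / ln(7/5) = 0.78
- velocity: (1/5 − 1/6.5) / (1/5 − 1/7) = 0.81

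**Step 2, simulation.** Two separate simulations, both with decline generated on velocity at a true ratio of 0.75:
- A: 10-m test, 3,000 trials of 45 v 90, loss 6% placebo v 3.5% treated.
- B: a timed test with median baseline 4.5 s, 2,000,000 per arm, loss 7.1% v 4.3%.

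| Handling of inability | A | B |
|---|---|---|
| Seconds, cap 20 s | 0.723 | 0.715 |
| Seconds, cap 30 s | 0.691 | 0.687 |
| Seconds, cap 45 s | 0.662 | 0.665 |
| Seconds, cap 60 s | 0.644 | 0.652 |
| Velocity, 0 | 0.759 | 0.753 |

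In A, the caps move the slowing from 1 − 0.723 = 28% to 1 − 0.644 = 36%; velocity with 0 gives 24%. Treating inability as missing and imputing it gives 0.713 in seconds and 0.774 on velocity. Loss falls by (6 − 3.5) / 6 = 42%, more than the 25% slowing, so a larger cap enlarges the ratio effect. For the 4-stair climb at 6% loss, the caps give 0.743 to 0.698.

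As a difference in seconds on the 10-m test, the caps matter more: 0.84 / 0.38 = 2.2-fold at 3% placebo loss and 2.50 / 0.85 = 2.9-fold at 13%. The planned effect measure, however, is the rate ratio.

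**Step 3, no drug effect.** At 6% loss, all ratios were 0.99 to 1.00, and each of seven options gave at most 2.3% false positives at one-sided 2.5%. Choosing the best of seven after the fact gave 3.5% to 3.8%.

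**Step 4, what the NSAA text already supplies.** Section 11.3.2.2 names loss of ability among the sources of missing data, gives an imputation rule for missing values, and makes an exception only where the NSAA has a natural 0. Where no such 0 exists, an analyst can leave the imputation rule in force. The constraint is reversed for seconds or kept for velocity. Because the model treats baseline as an outcome with a patient-specific intercept, a missing Day 1 stair time does not by itself remove a boy from the ITT analysis.

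**The case for a change.** The strongest case for a change is that it is cheap and that the choice is visible in the results. Two or three sentences would settle scale, sign and inability rule. The text supports two readings, worst value or imputation. With a true ratio of 0.75, the seven options disagreed on significance in 22% to 26% of trials, and the four caps alone in 4% to 8%. Simulation B, in trials of 45 v 90, found 39.2% significant on velocity with 0 against 5.6% to 14.6% in seconds with a cap.

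It stands that the protocol does not state the rule, that two readings exist and that they yield different estimates. The power contrast does not stand as a reason to prefer velocity. Decline was generated on velocity, so that scale was favoured by construction. Velocity with 0 also has costs: values pile up at 0, the normal-error fit suffers, and a boy already at 0 cannot decline further. Nothing suggests a choice made with knowledge of allocation. Section 7.1 keeps study personnel blinded to the double-blind assignment until the end of the study, and section 11.5 keeps interim results from sponsor staff running the trial. The protocol also points to a SAP for thresholds and a Study Manual for the functional tests. What they say on these two tests could not be checked here.

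**Conclusion.** This is a gap that analysts can fill sensibly, and no change to the plan follows. The omission concerns how to write down a convention for two non-key secondary endpoints. These are outside the family-wise error control in section 11.3.3, drive no interim decision and play no part in the sample size. Lost function is still captured by the NSAA and by the loss-of-ambulation milestone. No option is biased if the drug has no effect, and none was shown to be better if it works.

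The size, if the drug works, is an apparent slowing on the 10-m test of about 28% to 36% across caps of 20 to 60 s, against about 24% on velocity with 0, at 6% placebo loss and a true ratio of 0.75. The loss rates, caps and velocity distributions are assumptions. The ratio of mean declines stands in for the planned Bayesian rate ratio, which was not fitted. Inability at baseline on the stairs was excluded from simulation A by its baseline limits, so that part rests on reading the model and not on numbers.
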